Participation in the study does not imply receiving monetary, other material compensation, or any other direct benefit for the subject. However, the participant will have the opportunity to receive the study drug Ingaron®, registered for medical use in the Russian Federation for indications of prevention and treatment of acute respiratory viral infections. During the study, study group participants will receive 2 vials of the drug based on 2 cycles of 10-day prevention. Participants of the control group will have the opportunity to receive 1 bottle of the drug upon

² It was noted in patients receiving complex therapy for hepatitis B, C, as well as in the treatment of oncological diseases

³ It was noted in patients who received the drug as part of chemotherapy for oncological diseases

⁴ It was noted in patients receiving the drug with disseminated melanoma of the skin

⁵ It was noted in patients receiving complex therapy for hepatitis B, C, as well as in the treatment of disseminated melanoma

⁶ It was noted in patients receiving complex therapy for hepatitis C, as well as in the treatment of oncological diseases

* It was noted with the same frequency in patients who received the drug as part of chemotherapy or who received only chemotherapy

** It was noted with a lower frequency in patients who received the drug as part of chemotherapy, compared with patients who received only chemotherapy

completion of participation in the study for self-use within the instructions for medical use if they express a desire.

Introduction

The first coronavirus was isolated back in 1965 from a patient with SARS. But it has been of particular interest since the early 2000s, when the first outbreaks of coronavirus infections with fatal outcomes began. To date, science knows 37 types of RNA-containing coronaviruses.

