Randomization of the study participants is carried out on the same day or the next day after signing the informed consent, but no later than 3 days from the date of material sampling to the PCR test.

Randomization is carried out according to the Randomization List version 1.00 from 16.11.2020. To randomize a participant into a study, a research physician must contact the employee responsible for randomization (instructions for randomization are provided by the sponsor to the center before the start of the study) by phone and provide the study code and the researcher's full name for identification, as well as the data of the randomized participant: screening number, initials, date of birth. The researcher is informed of the assigned randomization number of the participant and the number of the prevention group (I or II). After the call, a Randomization Form is sent to the researcher's email as confirmation. The form must be printed out, signed by the researcher, and attached to the primary documentation of the participant.

The intake of the study drug is carried out independently by the participant at home, with the Diary of the participant of the study.

Other preventive measures

Any non-specific measures for the prevention of a new coronavirus infection COVID-19 are allowed, including personal protective equipment (respirators, glasses, gloves, protective suits).

Previous therapy

As a previous therapy, it is prohibited to take any drug with test status 1 month before participating in this study.

Concomitant therapy

According to the design of the non-interventional study, participants can receive any concomitant therapy for concomitant chronic diseases, except medications prescribed off-label or for research purposes.

Prohibited therapy

For the study group: use of any medications that may or may have preventive effects against ARVI, including COVID-19, is **prohibited**; use of non-specific methods of preventive protection is **not prohibited**.

For the control group: use of interferon gamma is **prohibited**; use of any medications that may or may have preventive effects against ARVI, including COVID-19, as well as the use of non-specific methods of preventive protection is **not prohibited**.

All preventive measures, including pharmacotherapeutic ones, should be indicated in the diary filled in by the participant.

Exclusion criteria

A participant should be excluded from the study if at least one of the following criteria is met:

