1. The use of the prohibited therapy indicated above, specific to each of the groups.
2. Withdrawal of informed consent.
3. Compliance to the study therapy is 50% or less.
4. Systematic non-compliance with protocol procedures by the participant.
5. Development of individual intolerance to the study drug (for the study group).
6. The development of concomitant diseases or conditions that, according to the researcher, may distort the results of the study, restrict the rights of the volunteer or put him at greater risk.
7. The appearance of contraindications to the use of the study drug in the period before the last intake of the second 10-day cycle (for the study group).
8. Participation in a clinical trial using a different therapy.
9. Disagreement on following reliable contraceptive measures (sexual abstinence; or a combination of 2 different methods: for example, barrier and spermicides, or barrier and intrauterine device, or barrier and hormonal, etc.) – for participants with preserved childbearing potential in the period before the last intake of the second 10-day cycle (for the study group).
10. Pregnancy.

A woman who excluded from the study due to the onset of pregnancy during the clinical trial is subject to medical supervision during the entire period of pregnancy, as well as for 6 months postpartum period to assess the condition of the woman and the born child (observation is carried out if possible and only if her desire and consent to such observation is mandatory). Information about the course of pregnancy and its outcome is entered in the primary documentation (with the consent of the woman). During the entire period of pregnancy, together with an obstetrician-gynecologist (with the consent of the pregnant woman and, if possible, contact with a doctor), observing a woman, her general condition, data reflecting the nature of the course of pregnancy, results of laboratory and instrumental examination methods, including ultrasound, are analyzed. Monitoring of the born child is carried out with the consent of the woman together with the district pediatrician (if possible, contact with him) until the child is 6 months old to analyze the clinical status of the child, data from laboratory and instrumental research methods.

There are no procedures for replacing excluded participants.

Diaries of participants

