1. The proportion of patients with confirmed COVID-19 at the end of the period of preventive treatment of the drug (measurement period: 28 days).
2. The proportion of patients with acute respiratory viral infections, including COVID-19, at the end of the follow-up period (change period: 2 months).
3. The proportion of patients with confirmed COVID-19 at the end of the follow-up period (change period: 2 months).
4. Frequency of development of complicated course of ARVI.
5. The proportion of participants with each of the scores (0-8) according to the WHO Clinical Improvement Scale (change period: 28 days).
6. The proportion of participants with each of the scores (0-8) according to the WHO Clinical Improvement Scale (change period: 2 months).
7. Duration of symptoms of the disease of study participants who had acute respiratory viral infections, including COVID-19 (change period: 2 months).
8. The duration of the symptoms of the disease of the study participants who were infected with ARVI, including COVID-19 (measurement period: 28 days).

Confirmation of clinical cases of ARVI, including COVID-19:

In the following cases:

- 1) a positive result of PCR on SARS-CoV-2 RNA, regardless of the presence of clinical symptoms;
- 2) appearance of clinical symptoms of ARVI in the absence of a PCR result on SARS-CoV-2 RNA or in the case of a negative result on SARS-CoV-2 RNA, -

at any stage during participation in the study, a completion visit (Visit 3) is conducted at the end of the quarantine period (at least 14 days from the date of signing Consent for the treatment of a new COVID-19 coronavirus infection in outpatient settings (at home) and compliance with the isolation regime or discharge from the hospital in case of laboratory confirmation of COVID-19), at which the patient returns the participant's diary and reports his condition to the doctor-researcher, transmits information about hospitalization, duration of symptoms, results of tests and performed studies.

Definition of the COVID-19 case:

Suspicious case of COVID-19

Body temperature above 37.5° in addition to one or more of the following signs (in the absence of other known causes that explain the clinical picture, regardless of the epidemiological history):

- Cough (dry or with scant sputum)
- Shortness of breath
- Feeling of congestion in the chest
- SpO₂ no more than 95%
- Sore throat
- Nasal stuffiness or moderate rhinorrhea
- Smell disorders or anosmia
- Ageusia
- Conjunctivitis
- Fatigue

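### Exclusion criterion 1 has no time window and no exception for medicines started after ARVI onset, so it can remove Group I cases, but not matching Group II cases, from the per-protocol sets

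*Protocol*

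**What the plan says.** The protocol's Exclusion criteria open with "A participant should be excluded from the study if at least one of the following criteria is met". Item 1 is "The use of the prohibited therapy indicated above, specific to each of the groups". The section Prohibited therapy defines what is meant:

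- Group I: "use of any medications that may or may have preventive effects against ARVI, including COVID-19, is" prohibited.
- Group II: "For the control group: use of interferon gamma is" prohibited. Other medicines with a possible preventive effect are expressly allowed.

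Neither section says when the prohibition ends, and neither mentions treatment of an ARVI that has already begun. Other items in the same list do carry a window; item 7, for example, reads "The appearance of contraindications to the use of the study drug in the period before the last intake of the second 10-day cycle", and item 9 has a similar limit.

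Other sections bear on what happens to a participant who falls ill:

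- The last paragraph of Nasopharyngeal smear keeps a participant with a positive PCR, during or after the course, in the study.
- Confirmation of clinical cases of ARVI sends PCR-positive cases and clinical cases alike to Visit 3, "at which the patient returns the participant's diary and reports his condition to the doctor-researcher". Main stages of the study allows that visit to move for ARVI cases and asks for information as complete as possible.
- Diaries of participants and Appendix 1 provide for recording ARVI treatment.
- SAP 5.5 makes ITT the main set whatever the compliance. PP requires completion without significant deviations and serves to test the sensitivity of the ITT result. SAP 5.3 analyses available data only.

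**The concern.** The Group I prohibition is defined by what a medicine may do, not by why it is taken. Preventive and therapeutic use can overlap: the protocol's Benefit section describes the study drug itself as registered "for indications of prevention and treatment of acute respiratory viral infections". Treating an ARVI can therefore amount to using prohibited therapy in Group I. The trigger is then the primary-endpoint event, and for most such medicines it operates in one arm only.

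If sites or the data review apply the criterion literally, Group I loses cases and Group II does not. The PP comparison would move toward the drug even if the drug did nothing, and agreement between PP and ITT would be weaker evidence than it looks. For an excluded participant, the outcomes collected later (2-month rates, symptom duration, WHO score) could also be missing, and no imputation is planned.

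**Working it through.** **1. Where 315 per arm comes from.** The protocol's formula in Number of participants, with 5% v 2% and t = 1.96:

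n = (0.05×0.95 + 0.02×0.98) × 1.96² / 0.03² = 0.0671 × 3.8416 / 0.0009 = 286.4, and 286 × 1.1 = 314.6, so 315.

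The plan's 286 and 315 reproduce. (The formula's lack of a power term is a separate matter and does not affect this point.)

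**2. The rule applied to three ARVI cases.**

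| Medicine started after onset | Group I | Group II |
|---|---|---|
| No possible preventive effect | Criterion 1 not met | Criterion 1 not met |
| Possible preventive effect, not interferon gamma | Criterion 1 met | Criterion 1 not met |
| Interferon gamma as treatment | Criterion 1 met on a literal reading | Criterion 1 met |

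Only the middle row differs between arms. For a PCR-positive Group I case in that row, Exclusion criteria and the end of Nasopharyngeal smear give opposite answers. For a PCR-negative or untested case, Exclusion criteria stands against the follow-up to Visit 3 described under Confirmation of clinical cases. The Concomitant therapy section does not settle it, because it speaks only of treatment for chronic conditions.

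**3. Which analyses are exposed.** An excluded participant has not completed without significant deviations, so leaves PP and its two vaccination variants, PP_NV and PP_NV_BE. ITT membership does not depend on compliance, and SAP 5.1 collects cases on a case form throughout the study. A 28-day case recorded there should still count. Outcomes after exclusion have no such protection.

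**4. Size, for PP only.** Inputs: no drug effect; incidence p = 5% in both arms (the top of the protocol's 1 to 5% range); 315 per arm. A share f of Group I cases is removed. **f is an assumption; the documents do not give it.**

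- Expected cases per arm: 0.05 × 315 = 15.75; removed from Group I: 15.75 × f.
- Apparent Group I rate: p(1−f) / (1−pf). For f = 25%: 0.0375 / 0.9875 = 3.8%.
- Rejection rate: 400,000 simulated trials, Pearson chi-squared without correction, two-sided 0.05.

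| f | Cases removed | Apparent Group I rate (Group II 5.0%) | Two-sided rejection |
|---|---|---|---|
| 0 | 0 | 5.0% | 5.1% |
| 10% | 1.6 | 4.5% | 5.9% |
| 25% | 3.9 | 3.8% | 11.3% |
| 50% | 7.9 | 2.6% | 35.6% |

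At f = 25% and 50% nearly all rejections favour the drug (11.0% and 35.6%). Using the SAP's own choice among Fisher, Yates-corrected and plain chi-squared tests, favourable rejections are about 2.5%, 10 to 11% and 33.5% at f = 0, 25% and 50%. With 286 per arm they are about 10% and 30% at f = 25% and 50%.

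**The case against.** The strongest reply is that the plan already says what to do with cases. PCR-positive participants stay, whatever they take, and all registered cases go to Visit 3. The Group I diary has a therapy column beside ARVI symptoms, which suggests treatment is expected rather than a cause of exclusion. Prohibited therapy closes by asking participants to record preventive measures, which fits a reading limited to prophylaxis. The schedule marks the check of exclusion criteria at Visit 2 only, the same contact as the first effectiveness evaluation, so the 28-day outcome should be known when exclusion is considered.

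Much of this stands, and it rules out three stronger conclusions that a reader might draw:

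- *Every Group I participant who treats an ARVI must be excluded.* Medicines without a possible preventive effect are not barred, and other sections point toward keeping cases.
- *Such cases lose Visit 3.* The case-follow-up rules say otherwise; the documents conflict rather than settle it.
- *The primary result is biased.* Populations for analysis and SAP 5.1 and 5.5 make the intention-to-treat set the main one. Number of participants does call PP the primary analysis population, but that is a separate inconsistency, and the other sections contradict it.

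The study drug is also a poor example of the asymmetry, since interferon gamma is barred in Group II too.

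What the reply does not remove is the wording of criterion 1 itself. It says users should be excluded, it has no window although items 7 and 9 do, and it differs by group. Sites could apply it differently.

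**Conclusion.** The point holds as an unreconciled conflict with a one-sided consequence. Criterion 1, as written, can take endpoint cases out of Group I in the drug's favour. The direct effect is on PP, PP_NV and PP_NV_BE, and on outcomes recorded after exclusion. The 28-day ITT count is largely protected, provided the case form is completed and used.

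The size depends entirely on f. At 10% the distortion of PP is slight (5.9% v 5.1%); at 25% the error rate is roughly doubled; at 50% it is about 36%. These figures assume 5% incidence, no drug effect and removal in Group I only. At 1% incidence there would be only 0.01 × 315 = 3.15 cases per arm to lose. Higher incidence gives larger figures (about 74% at 14% and f = 50%), but the protocol takes 14% from medical workers at high exposure, not from its planned 1 to 5%, so that should not be the headline.

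Should-fix, not must-fix: the main analysis has a safeguard, but the stated sensitivity analyses do not.

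**What to change.** Reconcile Prohibited therapy and Exclusion criteria with the schedule, the end of Nasopharyngeal smear and Confirmation of clinical cases of ARVI. Then add:

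- In criterion 1 and in the SAP 5.5 definition of PP: a medicine started after onset of a registered ARVI is not, by itself, a reason in either group for exclusion from the study or removal from PP. Other major deviations still apply.
- In both documents: every registered case keeps Visit 3 and counts in ITT.

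The same PP wording should carry over to PP_NV and PP_NV_BE. This concerns study participation and analysis-set membership only, not what treatment an ill participant receives.

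The cost is a few sentences and no new visits or tests. The Appendix 1 table has one pair of dates per row for complaints and therapy together, so it is worth confirming that the ARVI case form records a start date for each medicine; otherwise onset and start of therapy may be hard to order.

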In case of a positive PCR test before the start of the drug, volunteer is not included in the study, is isolated and falls under the supervision of a district doctor. In case of a positive PCR test during or after the preventive course, volunteer continues to participate in the study, is isolated under observation and, if possible, comes to visit 3 after the quarantine is lifted (at least 14 days from the date of signing Consent for the treatment of a new coronavirus infection COVID-19 in outpatient conditions (at home) and observing the isolation regime or discharge from the hospital in case of laboratory confirmation of COVID-19) with the provision of data on their condition to the researcher coordinator.

STUDY POPULATION

Adult volunteers who do not have clinical symptoms of ARVI.

Inclusion criteria

1. Volunteers of both genders over 18 years old.
2. Obtaining a written form of informed consent.
3. Ability and consent to participate in this study.
4. No symptoms of respiratory infection.
5. A negative result of a PCR study for the presence of SARS-CoV-2 RNA according to the biomaterial obtained by nasopharyngeal ⁹smear.

Non-inclusion criteria

1. Any other concomitant diseases or conditions that, in the opinion of the research doctor, may distort the results of the study, restrict the rights of the volunteer, or put him at greater risk.
2. Contraindications to the use of the study drug.
3. Individual intolerance of the ingredients included in the composition of the study drug.
4. Pregnancy or breast-feeding.
5. Controversial result of PCR test for the presence of SARS-CoV-2 RNA according to the biomaterial obtained by nasopharyngeal smear.
6. Participation in a clinical trial using the investigated therapy for 30 days prior to inclusion in this study.
7. Disagreement on following reliable contraceptive measures in the framework of the study

⁹ It is permissible to accept the results of a nasal or pharyngeal smear, as well as the results of studies performed before inclusion in the study for no more than 72 hours.

(sexual abstinence; or a combination of 2 different methods: for example, barrier and spermicides, or barrier and intrauterine device, or barrier and hormonal, etc.) – for participants with preserved childbearing potential.

Number of participants

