2.3. Blinding procedure

This study is open-label.

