5.3. Missing / incorrect data

For all parameters, the analysis will be carried out only on the available information, without filling in the data. There are no plans to use data reconstruction methods in this study.

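### Exclusion criterion 6 lets a researcher who knows the group remove a randomised participant whose new illness might distort the results, with no exception for respiratory illness

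*Protocol*

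**What the plan says.** The Protocol's list of exclusion criteria opens with a firm rule: "A participant should be excluded from the study if at least one of the following criteria is met". Item 6 of that list is "The development of concomitant diseases or conditions that, according to the researcher, may distort the results of the study". The same item has two further limbs, on the volunteer's rights and on risk, which are not at issue here. The item gives no list of conditions, asks for no independent review and makes no exception for respiratory illness.

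The researcher applies it with the allocation known. SAP 2.3 states "This study is open-label", and the Protocol's randomisation section has the researcher told the participant's group by telephone.

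The Protocol's schedule of procedures marks the check of exclusion criteria at one visit only, Visit 2. This is the telephone contact at the end of the preventive course, where effectiveness is also evaluated. Neither a physical examination nor a SARS-CoV-2 test is marked there.

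The case rule, in the Protocol's text on confirming clinical cases and again in SAP 3.2, covers a positive PCR and also "appearance of clinical symptoms of ARVI in the absence of a PCR result on SARS-CoV-2 RNA or in the case of a negative result". The section on the nasopharyngeal smear adds: "In case of a positive PCR test during or after the preventive course, volunteer continues to participate in the study". On missing data, SAP 5.3 says that "the analysis will be carried out only on the available information, without filling in the data".

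**The concern.** Before randomisation, a criterion of this kind is ordinary, and non-inclusion criterion 1 has almost the same content. After randomisation, in an open-label trial, it permits exclusion by someone who knows the group and is asked to consider the effect on the results.

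The boundary with the endpoint is also soft. COVID-19 has suspicious, probable and confirmed definitions, but other ARVI has no symptom list and no adjudication. A PCR-negative or untested rhinitis or febrile illness can be read as an ARVI case or as a concomitant condition. Nothing in the exclusion criteria says which reading prevails.

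If the second reading were chosen more readily in Group I than in Group II, the trial could show a benefit that the drug does not have.

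**Working it through.** **1. Where an excluded illness goes**

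| Situation | What the documents do with it |
|---|---|
| PCR-positive after randomisation | Stays in the study and is a case |
| ARVI symptoms, PCR negative or absent, registered | A case at any stage (Protocol case rule, SAP 3.2); kept in ITT whatever the compliance (SAP 5.5) |
| Respiratory illness labelled concomitant and excluded before registration | No case on record; nothing filled in (SAP 5.3) |
| ARVI arising after a criterion 6 exclusion | No efficacy follow-up after exclusion is described; nothing filled in |
| Any participant excluded early | Lost from PP |

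The last row carries more weight than it should, because the documents disagree on the role of PP. The Protocol's section on the number of participants calls PP the population of the primary analysis. The Protocol's statistical methods and SAP 5.1 make the FAS/ITT set the main one.

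**2. How many cases are expected**

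The plan's formula, with P1 = 0.05, P2 = 0.02 and t = 1.96, gives

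n = (0.05×0.95 + 0.02×0.98) × 1.96² / 0.03² = 0.0671 × 3.8416 / 0.0009 = 286.4 per group,

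and 286.4 × 1.10 = 315. This reproduces the stated 286 and 315. Expected cases at 286 per group are 0.05 × 286 = 14.3 and 0.02 × 286 = 5.7, so about 14 v 6.

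**3. What one case can do** (two-sided Pearson test; all expected counts above 10)

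- 16 v 7 of 286: expected 11.5 per group; χ² = 2×4.5²/11.5 + 2×4.5²/274.5 = 3.67; p = 0.055.
- 16 v 6 of 286: expected 11 per group; χ² = 2×5²/11 + 2×5²/275 = 4.73; p = 0.030. With 285 in Group I it is still 0.030.

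This holds near the boundary and not everywhere. At 14 v 6 of 286, p = 0.069. With one Group I case removed (5 of 285 v 14 of 286), the SAP rule moves to the Yates correction and p = 0.063.

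**4. Illustration of differential exclusion**

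Assumptions: no drug effect; 286 per group; the SAP rule (Fisher below an expected count of 5, Yates from 5 to 10, otherwise Pearson); a share q of Group I illnesses removed from both cases and denominator. Chance of a significant result favouring Group I:

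| Incidence in both groups | q = 0 | q = 10% | q = 20% | q = 30% |
|---|---|---|---|---|
| 5%, exclusion in Group I only | 2.4% | 4.4% | 7.6% | 12.5% |
| 8%, exclusion in Group I only | 2.5% | 5.1% | 10.0% | 18.2% |
| 5%, same q in both groups | – | 2.4% | 2.2% | 1.9% |
| 8%, same q in both groups | – | 2.5% | 2.5% | 2.5% |

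The 5% rate is the top of the Protocol's assumed control range of 1 to 5%; 8% is a further row of its Table 1. The documents give no value for q.

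**The case against.** The strongest reply is that the documents treat the endpoint illness as something to follow, so concomitant naturally means other diseases. Much supports this. The case rule covers PCR-negative and untested symptoms. Participation may be extended to 90 days for someone with ARVI. Respiratory symptoms are kept out of the adverse events and analysed for effectiveness, and so are hospitalisation, death or life threat from ARVI complications. Symptoms are also entered in the participant's own diary. A reader might infer from the smear section that only PCR-positive illness is protected; the case rule does not support that.

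A reader might also see item 8, "Participation in a clinical trial using a different therapy", as a second exit driven by the outcome. It involves no judgement about an illness, and a case registered before the participant joins another trial stays in ITT. It does not support the point.

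The reply is also right that SAP Table 1 already reports exclusions by criterion and group. It is right, too, that a researcher could leave an illness unregistered without excluding anyone, which a change to criterion 6 would not prevent.

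One thing survives all this. The case rule works only once the illness is called ARVI, and no text says that it overrides criterion 6. The Protocol separates the endpoint illness from adverse events and from urgent reporting, but not from the exclusion criteria.

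**Conclusion.** The point holds in a limited form. Criterion 6 gives an unblinded researcher a discretionary exclusion after randomisation with no respiratory exception. The exposure is a respiratory illness excluded before registration, efficacy data lost after exclusion, and loss from PP.

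The fragility is real: with about 14 v 6 cases expected, one case near the boundary changes the conclusion. The inflation to about 4–12% (5% incidence) or 5–18% (8% incidence) rests on an unsourced q of 10–30% acting in Group I only. It applies q to all illnesses, including the PCR-positive ones that the Protocol keeps. With equal exclusion the inflation disappears. The figures show what differential exclusion could do; nothing in the documents shows that it is planned or likely.

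A reader might infer that the main analysis is open to removal of cases at will. It is not: a case already registered counts in ITT. The change is worth making because the gap can be closed with a few words.

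**What to change.** 1. In criterion 6, delete the limb about distorting the results. Leave the limbs on rights and risk unchanged.
2. Add that symptoms of ARVI or COVID-19 and their complications after randomisation are endpoint data under the case rule (Protocol, confirmation of clinical cases; SAP 3.2), are registered on the ARVI case form, and are not a ground for exclusion on account of distorting the results. This concerns follow-up and analysis status only and sets no clinical rule.
3. State in SAP 5.5 that no participant leaves ITT or PP for that reason.
4. In SAP Table 1, add the diagnosis to the existing line for exclusions under criterion 6.

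The cost is wording in the two documents, with no extra visits or participants. The small downside is that a few participants with confounding conditions stay in the analysis. The change does not supply a symptom definition or blinded adjudication for ARVI other than COVID-19. It also leaves open which set is primary, which the Protocol and SAP need to reconcile.
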